Specific Aim 1 (Phase II): Informed by Phase I findings, (approved in a previous IRB protocol #2016P000423), we aim to develop and determine the feasibility (by assessing the number of sessions attended and adherence to Relaxation Response practice) and acceptability (assessed using the Participant Feedback Survey) of an 8-session Relaxation Response Resiliency (SMART-3RP) program for parents of children with learning disabilities.

Hypothesis: The SMART-3RP virtual delivery will be feasible to implement and acceptable to parents of children with learning disabilities.

Primary Aim 2 (Phase III): To test the effectiveness of a pilot waitlist controlled trial on improving resiliency, as measured using the General Self-Efficacy Questionnaire, Current Experiences Scale, and the Visual Analogue 0-10 scales (including stress, distress, coping, and physical discomfort), and on improving stress reactivity (as measured by the Measure of Current Status-A), growth enhancement (as measured by the Cognitive and Affective Mindfulness Scale-Revised), and parental stress (as measured by the Parental Stress Scale). This will be assessed by comparing Baseline-3 mo. scores on primary and secondary outcome measures between the Immediate and Waitlist control groups.

Primary Hypothesis: Patients randomized to the Immediate group will report significantly greater scores on the primary outcomes (measures of resilience) and on the secondary outcomes (measures of stress reactivity, growth enhancement, and parental stress) at 3 mo. post enrollment.

Secondary Aims: Among participants randomized to both conditions, to investigate the extent of pre-post changes in primary and secondary outcomes (Immediate: assessments from baseline-3 mo.; Waitlist: from 3-6 mo.).

Secondary Hypothesis: Scores on primary and secondary outcome measures will improve from pre-post intervention.

Secondary Aim 2: Among immediate condition group only, to assess whether end-of-treatment (3 mo. post enrollment) improvements will be sustained at 6-mo. post enrollment.

Hypothesis: These end-of-treatment effects will show sustained improvement on primary and secondary outcome measures from 3 to 6-mo. Post enrollment.

Secondary Aim 3: To pilot test the end-of-treatment effects of the SMART-3RP on parents' stress levels using hair cortisol. A mixed effects models approach will be used to examine group

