differences in hair cortisol concentrations (HCC) at baseline and 3 mo. post enrollment. Pearson correlation or Spearman's rank correlation will be used to examine the association of HCC with each of our psychological outcomes.

Hypothesis: Parents randomized to the Immediate group will show improvements in biomarkers of stress system function, in particular the hypothalamus pituitary adrenal (HPA) axis and sympathetic nervous system (SNS) relative to baseline. It is expected that stress-related alterations will be found in parents before the intervention and will improve in those individuals that respond favorably to the treatment. Biomarkers will thus allow an additional level of testing for chronic stress, and efficiency of the intervention; measuring basal HPA axis and SNS activity further allows us to draw conclusions about the adverse long-term health effects of chronic stress and to evaluate the efficiency of the intervention in ameliorating such biological changes.

III. SUBJECT SELECTION

We will recruit through our contacts in the community including other MGH clinicians, as well as through local and national support groups and list serves using IRB approved recruitment materials. MGH child psychologists may also refer potentially eligible participants. Interested participants may call or email the study staff to learn more about the study.

The current study will employ a pretest-posttest, pilot waitlist controlled design to test the 3RP for parents of children with learning disabilities. Participants will be recruited from local, national, and international organizations, school systems, and hospital clinics.

Inclusion/Exclusion Criteria

Inclusion criteria are:

- 1) Being the parent of at least one child with a learning disability
- 2) Age 18 or older
- 3) Can read and speak English

One or more of the following exclusion criteria will render an individual ineligible:

- 1) Being the parent of a child with a severe mental or physical disability up to the discretion of the principal investigator
- 2) Regular use of corticosteroids at the discretion of the Principal Investigator
- 3) Unable or unwilling to sign the informed consent documents
- 4) Unable or unwilling to participate in an intervention delivered via videoconferencing.

Recruitment

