Study assessments include a battery of questionnaires via REDCap and two hair cortisol sample collections. At baseline, participants will be administered baseline questionnaires and asked to provide a hair cortisol sample. At 3 months post enrollment, participants are administered a second set of questionnaires, and asked to complete a second hair cortisol sample. At 6 months post enrollment, participants are administered their final set of questionnaires.

Hair Cortisol

At enrollment (baseline) as well as at 3 months post enrollment, all participants will be asked to provide a hair sample to measure potential changes in cortisol levels, a method used successfully in stress studies. Participants will be asked to cut a small amount of hair (approximately 150 strands, which is about the diameter of a small paperclip) as close to the scalp as possible (about 3 cm), and from the back of their head. They will be asked to band or tie the strands near the scalp end, place on the sample in aluminum foil, and return in an envelope to MGH. Participants will be sent detailed sampling instructions and stamped, addressed envelopes to facilitate mailing. We are going to ask participants whether they regularly take corticosteroids because they may interfere with the accuracy of the hair cortisol sample.

The assessments are itemized below. In addition, participants will be asked to complete practice notes throughout their intervention.

Administered at Baseline:

3RP Battery of questionnaires
Hair Cortisol Sample

Administered 3 months post enrollment:

3RP Battery of questionnaires
Hair Cortisol Sample

Participant Feedback Questionnaire

Administered during Intervention (either starting after baseline or 3 months post enrollment)
Progress Note

Administered 6 months post enrollment

3RP Battery of questionnaires

Participant Feedback Questionnaire

[figure not shown]

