Acceptability will be assessed using a Participant Feedback questionnaire (See Feedback questionnaire attached).

2) Is the virtual SMART-3RP program effective for parents of children with learning disabilities?

a) Is there a significant difference in primary and secondary outcome measures between participants in the Immediate and Waitlist SMART-3RP groups at 3 mo. post enrollment?

We will use paired samples t-tests to compare within group differences on primary and secondary outcome measures from 3 mo. to baseline for the Immediate and Waitlist Groups. Primary outcome measures are the General Self-Efficacy Questionnaire (GSE), Current Experiences Scale (CES; from the Post Traumatic Growth Inventory), and the Visual Analogue 0-10 scales (VAS; measuring stress, distress, coping, and physical discomfort). Secondary outcome measures are: the Measure of Current Status-A (MOCS-A; to assess stress reactivity), Cognitive and Affective Mindfulness Scale-Revised (CAMS-R; to assess growth enhancement), and the Parental Stress Scale (PSS; to assess parental stress).

We will then use independent samples t-tests to compare the difference between the Immediate group's 3 months post enrollment and baseline assessment results with the

difference between the waitlist group's 3 months and baseline assessment results on primary and secondary outcome measures.

b) Among participants randomized to both conditions, will there be improvements in primary and secondary outcome measures from pre-post SMART-3RP (IG: assessments from baseline-3 mo.; WG: from 3-6 mo.)?

We will use paired samples t-tests to compare all primary and secondary assessments from pre-post SMART-3RP (for the IG, assessments are from baseline-3 mo.; for the WG, assessments are 3 mo. to 6 mo.).

c) Among the Immediate group only, will the changes from baseline to 3 months post enrollment (end of treatment) be sustained at 6 months post enrollment (3 months post treatment)?

We will use paired samples t-test to assess within-group differences in long-term outcomes. We will compare measures at the 6 months assessment to measures at the 3 months assessment for the Immediate group.

3) Will the virtual delivery SMART-3RP be effective in reducing participants' stress levels, measured by hair cortisol?

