A mixed effects models approach will be used to examine differences in hair cortisol concentrations (HCC) at enrollment (baseline) and at 3 months post enrollment for each study arm. Pearson correlation or Spearman's rank correlation will be used to examine the association of HCC with each of our psychological outcomes.

VII. RISKS AND DISCOMFORTS

Participants may feel uncomfortable completing various psychosocial questionnaires. As in any research study, there is a small risk that confidentiality may be breached; all efforts to minimize this risk will be taken, as outlined below. In addition, participants may find it time consuming to practice techniques learned in the intervention or tracking behavior such as elicitation the relaxation response.

Hair cortisol collection: some participants may feel uncomfortable sending us a hair sample. If they feel this way, they will not need to. Participants can still remain in the study if they do not wish to send a hair cortisol sample.

VIII. POTENTIAL BENEFITS

Participants in the current study may observe a reduction in symptoms of parental stress. It is hoped that the intervention will result in a statistically significant reduction of symptoms across these domains.

The current study may provide support for parents of children with learning disabilities. This intervention may enhance our understanding of the role of mind-body interventions such as the SMART-3RP in parents of children with learning disabilities. This intervention may have widespread implications for types of resources available that may ultimately improve health and well being of parents and children with learning disabilities.

IX. MONITORING AND QUALITY ASSURANCE

All study staff will complete required Partners human subjects trainings prior to the start of study procedures. All interventionists and assessors will have advanced training in interviewing and assessment. Participants will be informed that they may refuse to answer questions that make them feel uncomfortable. Participants will be advised to wear headphones and sit in a quiet place during each virtual session. Participants will also be asked not to share the contents of the group with anyone else.

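### Hair cortisol is described with three different comparisons, none specifies the between-arm difference in change as the test, and the SAP has no hair cortisol analysis

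*Protocol*

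**What the plan says.** The protocol deals with the hair cortisol comparison in four places.

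- **Section VI, question 3** sets an effectiveness question: "Will the virtual delivery SMART-3RP be effective in reducing participants' stress levels, measured by hair cortisol".
- **Section VI, analysis under question 3** applies a mixed effects model to HCC at enrolment and "at 3 months post enrollment for each study arm".
- **Section II, Secondary Aim 3** states the same model differently. The sentence begins "A mixed effects models approach will be used to examine group" and continues "differences in hair cortisol concentrations (HCC) at baseline and 3 mo. post enrollment". The object here is a difference between groups.
- **Section II, hypothesis for Secondary Aim 3**: "Parents randomized to the Immediate group will show improvements in biomarkers of stress system function". The comparator comes at the end of that sentence: "sympathetic nervous system (SNS) relative to baseline". The Waitlist group is not mentioned.

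Hair is requested from both arms at both times (Section V, Hair Cortisol): "all participants will be asked to provide a hair sample to measure potential changes in cortisol levels". Giving a sample is optional (Section VII): "Participants can still remain in the study if they do not wish to send a hair cortisol sample".

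The SAP, under Statistical Analyses, limits its efficacy work to psychosocial outcomes. It mentions neither hair cortisol nor a mixed model, and it does not say that the aim was withdrawn or is reported elsewhere.

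**The concern.** A mixed model is a framework, not a test. Fitted to two arms at two times, it can yield the change in Immediate, the change in Waitlist, the arm difference at baseline, the arm difference at 3 months, and the difference between the two changes. Only the last of these, or a baseline-adjusted arm difference at 3 months, uses randomisation to answer question 3.

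The wording of Section VI and of the hypothesis leads towards the change within an arm. Season, assay batch or regression to the mean can move HCC in both arms alike, and a within-arm change cannot separate such a drift from an effect of the programme. The Waitlist arm is there to remove it, and it is asked for the same two samples.

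With three descriptions in the protocol and none in the SAP, the contrast could also be chosen after the results are seen.

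**Working it through.** **1. The sections side by side**

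| Place | Comparison described | Uses Waitlist as comparator? |
|---|---|---|
| Section VI, question 3 | Effectiveness of the programme on HCC | Needs it |
| Section VI, analysis | Baseline and 3 months, by arm | Not stated |
| Secondary Aim 3 | Group differences at baseline and 3 months | Yes, but no difference in change is defined |
| Aim 3 hypothesis | Immediate group against its own baseline | No |
| SAP | No HCC analysis | n/a |

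For the questionnaires, Section VI question 2(a) takes two steps: paired tests within each group, then an independent-samples t-test of one group's change against the other's. HCC is not in the list of primary and secondary measures given there, so that second step does not cover it.

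**2. What a within-arm reading could cost**

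The documents give no alpha, effect size, SD or sample size for HCC, so there is no figure to reproduce. The following is an illustration.

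Inputs from the documents:
- About 70 participants (Section III, Recruitment), randomised 1:1 (Section IV): 70 / 2 = 35 per arm.
- The 75% time 2 response in the SAP: 0.75 × 35 = 26.25, taken as 26 per arm.

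Assumptions not in the documents:
- Two-sided 5% tests.
- No programme effect, and independent arms of equal size.
- The same true drift δ in both arms, towards improvement, in units of the SD of the change score.
- HCC numbers equal to full provision (35) or to the 75% response (26). Because samples are optional, true numbers may be lower.

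Formula: a paired t-test on n changes has a noncentral t distribution with n − 1 degrees of freedom and noncentrality δ√n. Let p be the probability that one arm shows a significant improvement. By independence, the probability that Immediate improves significantly and Waitlist does not is p(1 − p). The chance of a significant change in the wrong direction is below 0.2% in every row and does not alter the results at this precision.

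| n per arm | δ | δ√n | p | p(1 − p) |
|---|---|---|---|---|
| 26 | 0.2 | 1.02 | 0.164 | 0.137 |
| 35 | 0.2 | 1.18 | 0.209 | 0.165 |
| 26 | 0.3 | 1.53 | 0.312 | 0.215 |
| 35 | 0.3 | 1.77 | 0.407 | 0.241 |

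The misleading pattern therefore occurs in about 14% to 24% of trials. With no drift it is 0.025 × 0.975 = 0.024. The test of the between-arm difference in change stays at 5% for any common drift, because δ cancels.

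**3. What the between-arm contrast can detect**

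In SD units of change, the standard error of one arm's mean change is √(1/n) and that of the difference between arms is √(2/n), larger by √2 ≈ 1.41. At 80% power (assumed), the detectable difference is (1.960 + 0.842) × √(2/n): 0.67 SD at 35 per arm and 0.78 SD at 26.

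**The case against.** A reader might infer that the randomised comparison of HCC is absent from the plan altogether. The documents do not support that. Secondary Aim 3 says the model examines differences between groups, which is a between-arm phrase. A single mixed model holding both arms at both times would commonly include an arm-by-time term, and the by-arm wording in Section VI can be read as saying which data enter the model. Nor does the trial neglect its control arm elsewhere: the protocol tests between-arm change on the questionnaires, and the SAP makes that its main efficacy analysis. This stands, and it makes the fault one of inconsistency and an undefined contrast, not of a wrong contrast clearly chosen.

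A reader might also infer from the SAP that the cortisol aim was abandoned. The SAP restricts its efficacy section to psychosocial outcomes and does not withdraw the protocol's plan. Separate reporting is possible, though neither document says so.

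On size, it is tempting to quote the rate at which the Immediate arm alone would be significant under a common drift of 0.3 SD: 31% at 26 parents and 41% at 35. Those rates ignore the Waitlist change, which a by-arm analysis would also show and which would often reveal the drift. The 14% to 24% range takes that into account. The drift itself has no basis in the documents, and a smaller one would do less harm.

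Finally, this is a secondary aim in a pilot, with optional samples, so the stakes are limited. None of this supplies the missing definition of the test.

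**Conclusion.** The point holds as one of inconsistent description and omission. Three protocol statements point to different HCC comparisons, none specifies the between-arm difference in change as the test of question 3, and the SAP gives no HCC analysis.

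If Section VI and the hypothesis are followed as worded, a drift shared by both arms could pass for a programme effect. The 14% to 24% rests on assumed drift, assumed HCC numbers, independent arms and two-sided 5% tests; it shows the order of the risk and does not estimate it for this trial.

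This should be corrected, but it does not threaten the trial's main questionnaire comparison.

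**What to change.** 1. Reconcile Secondary Aim 3 with the analysis under question 3 in Section VI so that both describe the same comparison.
2. Name the arm-by-time term of the mixed model, that is, the between-arm difference in HCC change from baseline to 3 months, as the single HCC test.
3. Report the change within each arm descriptively, as means with confidence intervals and the number of parents with samples.
4. Restate the hypothesis as improvement relative to the Waitlist group.
5. Add this analysis to the SAP, or state there where HCC is reported. If HCC results were already known when the test was named, say so.

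The cost is wording only: the samples and the model stay the same. The downside is a wider interval than for a one-arm change, by a factor of about 1.41 with equal arms and equal SDs. With 26 to 35 per arm the contrast will detect only fairly large differences, so the interval should be presented as the main result.

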A total of approximately 70 participants will be recruited for this study. Both males and females from diverse racial and ethnic backgrounds will be recruited using IRB approved procedures. Potential participants will be recruited from our contacts in the community including other MGH

clinicians, as well as through local and national support groups and list serves using IRB approved recruitment materials. MGH child psychologists may also refer potentially eligible participants. In each case, interested participants will be directed to our pre-screen REDCap survey and will be given the option to contact the study staff to learn more about the study.

IV. SUBJECT ENROLLMENT

Methods of enrollment

Participants will contact the PI or study staff by telephone, email, or by completing our IRB approved pre-screen REDCap survey in response to advertisements. Subject will be contacted by phone, informed about the study and given a pre-screen REDCap to determine whether they meet inclusion/exclusion criteria (see the attached pre-screening questionnaire). Subjects may also be referred to the study. Subjects must respond “yes” to all inclusion criteria and “no” to all exclusion criteria to be eligible for the study. Eligible participants will be consented and will complete the baseline survey online into REDCap, a secure, web-based application designed to support data capture for research studies.

Randomization

After enrollment, participants will be randomized to the Immediate intervention group (IG) or Waitlist control group (WG). Randomization will be conducted using a random plan generator, with 1:1 randomization. The WG will begin their program approximately 3 months after the SMART-3RP group. For both groups, the intervention will last approximately 8 weeks, weekly with groups meeting once per week for approximately 1 hour.

Informed consent process

Eligible and interested participants will be sent a consent form and scheduled for a phone consent. Informed consent and authorization will be obtained and documented through use of a written consent form approved by the Partners Human Research Committee (PHRC) and signed by the participant. The PI or qualified study staff will complete informed consent procedures.

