In the SMART-3RP intervention, sessions focus on developing an understanding of stress physiology and the physiology of the relaxation response (RR), on developing a regular practice of eliciting the RR, and on learning cognitive behavioral and positive psychology/resilience skills. In addition to the weekly group sessions, participants will receive audio recorded guided meditations for independent relaxation practice. Participants are expected to practice eliciting the RR for approximately 20 minutes a day throughout the course of the study, using the audio recording provided and/or any other meditative or mind body techniques. Participants will complete a daily log reporting how often and by which methods they are practicing the RR. (Please see attached practice log).

Participants randomized to Immediate or Waitlist will participate in the SMART-3RP program. Participants in the Immediate arm will be encouraged to practice the skills taught in the program during the 3 month follow up period after completion of the 8 session SMART-3RP. Participants in the Waitlist arm will wait for approximately 3 months before beginning the SMART-3RP.

Participants in both groups will be given questionnaires at the same time points (baseline, 3 month post enrollment, and 6 month post enrollment). Study staff will email these questionnaires to the participants via the REDCap system. Participants who have not responded within two weeks of each time point will be contacted by telephone to ensure receipt of study data.

Figure 1 (below) illustrates the administration of questionnaires in both groups.

Figure 1. Study Design.

Baseline
T1

3 mo. Post
Enrollment
T2

6 mo. Post
Enrollment
T3

Remuneration

Participants will be given a \$20 gift certificate for completing 3 mo. survey and another \$20 gift certificate for completing the 6 mo. survey assessment.

VI. BIOSTATISTIC ANALYSIS

We plan to conduct a pilot trial of a virtual-based SMART-3RP intervention for parents of children with learning disabilities. Participants in this trial will be randomized to one of two groups: 1) Immediate SMART-3RP intervention, or 2) Waitlist control SMART-3RP group (starting approximately 3 months after enrollment).

The following questions will be assessed:

1) Is the virtual SMART-3RP feasible and acceptable for parents who have children with learning disabilities?

Feasibility will be assessed using attendance and homework completion (i.e. 6/8 sessions and homework completion).

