Electronic information will be stored in REDCap (Research Electronic Data Capture), a free, secure, and HIPAA-compliant web-based application hosted by the Partners HealthCare Research Computing Enterprise Research Infrastructure & Services (ERIS) group (based at the PHS Needham corporate datacenter).

REDCap (Research Electronic Data Capture) is a free, secure, HIPAA compliant web-based application hosted by the Partners HealthCare Research Computing Enterprise Research Infrastructure & Services (ERIS) group. The system offers easy data manipulation with audit trails, reports for monitoring and querying participant records, and an automated export mechanism to common statistical packages (SPSS, SAS, Stata, R/S-Plus).

Data will be stored on password protected computers that will be stored in secure locations at all times. Paper data files (with coded subject identification) will be stored in a locked filing cabinet. Only research staff will have access to these data locations.

A unique anonymous identifier will be assigned to each subject; subsequently, all data collected will be associated exclusively with this identifier. This includes all questionnaires administered over the course of the study, as well as home practice logs.

Data Management and Quality Control Procedures

To maximize accuracy and security, all survey data will be collected and stored on REDCap. Research staff will ensure that proper consent has been obtained before sending the REDCap survey to each participant.

Data and Safety Monitoring Plan

Adverse Event Monitoring: Throughout the study subjects will be monitored for the occurrence of events defined as any undesirable experience or unanticipated risk. Lack of effect of treatment is not considered an event. All adverse events will be reported on an adverse event form.

The principal investigator is ultimately responsible for data and safety monitoring. If study staff becomes aware of any adverse events, the event will be reported immediately to the Principal Investigator. The Principal Investigator has the responsibility of reporting serious adverse events (death, life threatening illness or injury, serious injury, or permanent disability) to PHRC within 72 hours of notification.

Subject Safety

In the case that an issue related to mandatory reporting or duty to warn arises, we will contact the Office of General Council for advice on how to proceed.

X. REFERENCES

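### Adverse-event monitoring is promised throughout, but no scheduled enquiry common to both arms is described and the SAP lists no harms summary, so any recorded count would be weak and possibly arm-biased evidence

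*Protocol*

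**What the plan says.** Protocol section IX, Data and Safety Monitoring Plan, makes a broad promise: "Throughout the study subjects will be monitored for the occurrence of events defined as any undesirable experience or unanticipated risk". It requires a form ("All adverse events will be reported on an adverse event form") and gives a reporting line: "If study staff becomes aware of any adverse events, the event will be reported immediately to the Principal Investigator". It ties no question, visit or interval to the form.

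Section V, Assessments, describes the scheduled data collection: "Study assessments include a battery of questionnaires via REDCap and two hair cortisol sample collections". The itemised list adds a participant feedback questionnaire at 3 and 6 months and a progress note whose timing depends on arm: "Administered during Intervention (either starting after baseline or 3 months post enrollment". A daily practice log is also kept.

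On contact, section IV (Randomization) says "the intervention will last approximately 8 weeks, weekly with groups meeting once per week for approximately 1 hour", and section V says "Participants in the Waitlist arm will wait for approximately 3 months before beginning the SMART-3RP". Both arms receive emailed questionnaires at baseline, 3 and 6 months. Those who have not replied within two weeks are telephoned so that the data are obtained.

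The SAP covers feasibility, acceptability, change scores between and within arms, maintenance, and a correlation of baseline parenting stress with change. It mentions neither adverse events nor individual worsening.

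**The concern.** If an event is recorded only when staff happen to learn of it, the count depends on how often staff and participant meet. In this design that differs by arm during the only period with a randomised untreated comparison. Equal true rates could then look unequal, with more events on the side that attends sessions, and an empty record could mean either few events or few opportunities to hear of them.

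A second gap compounds this. A favourable average change is compatible with some parents getting worse, and the SAP lists no summary that would show them. The protocol's background section names a national programme as the ultimate objective, so the pilot's record on harms is likely to be consulted later.

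**Working it through.** The documents state no adverse-event rate, safety sample size or detection probability, so there is no figure to reproduce. The check sets the promise against the planned routes and then illustrates what a count could show.

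**Step 1. Planned routes by arm and period** (protocol sections IV and V)

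| Period | Immediate arm | Waitlist arm |
|---|---|---|
| Baseline to 3 months | About 8 weekly group sessions, progress note, practice log; 3-month survey | No planned sessions; 3-month survey; call only if no reply |
| 3 to 6 months | No planned sessions; encouraged to keep practising; 6-month survey; call only if no reply | About 8 weekly group sessions, progress note, practice log; 6-month survey |

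Planned sessions are about 8 against 0 in the first period and 0 against about 8 in the second. The routes common to both arms are the surveys and the call to non-responders, and neither is described as asking about adverse events.

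**Step 2. What is collected equally in both arms.** The 0-10 visual analogue scales (VAS) include distress and physical discomfort. They and the Parental Stress Scale are outcome measures compared at the shared time points (protocol section VI). Worsening on them can be seen without depending on session contact. However, no worsening threshold is given, nothing links them to the adverse-event form, and the SAP plans no count of those who worsen.

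**Step 3. What zero recorded events would show.** Inputs: about 70 participants (section III, Recruitment) and 1:1 allocation, so about 35 per arm. With full capture, the exact one-sided 95% upper bound is 1 − 0.05^(1/n):

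- n = 70: 1 − 0.05^(1/70) = 4.2%
- n = 35: 1 − 0.05^(1/35) = 8.2%

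If only a fraction s of events is captured, the bound on the true risk is that figure divided by s. The values of s are assumptions, shown as a range:

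| s (assumed) | Bound, n = 70 | Bound, n = 35 |
|---|---|---|
| 1 | 4.2% | 8.2% |
| 0.5 | 8.4% | 16.4% |
| 0.25 | 16.8% | 32.8% |
| 0.1 | 41.9% | 82.0% |

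**Step 4. What unequal capture would do.** Assume the same 10% true risk in 35 people per arm and capture of 0.9 in the attending arm. The expected recorded count there is 35 × 0.10 × 0.9 = 3.15. In the waiting arm it is 35 × 0.10 × s:

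| s in waiting arm (assumed) | Expected recorded | Apparent ratio, 0.9/s |
|---|---|---|
| 0.9 | 3.15 | 1.0 |
| 0.5 | 1.75 | 1.8 |
| 0.25 | 0.88 | 3.6 |
| 0.1 | 0.35 | 9.0 |

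The ratio runs from 1.0 to 9.0 on assumption alone. It shows the direction of the bias, not its size in this trial.

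**The case against.** The case against is substantial, and several stronger readings fail.

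- **That no scheduled assessment asks about adverse events.** A reader might infer this from the list. The questionnaire battery, feedback form, progress note, practice log and adverse-event form are not reproduced, and the SAP mentions open-ended programme feedback. What can be said is that no such enquiry is described.
- **That a biased comparison is planned.** No aim, hypothesis or analysis compares adverse events between arms, and nothing says an empty record will be read as proof of safety. Both arms receive the programme, so the contact imbalance reverses after month 3. The point concerns any count that is later reported.
- **That waiting participants cannot be heard.** They have the 3-month survey, a call if they do not reply, study contact details and an invitation to ask questions at any time (section IV, Informed consent process). Equally, a one-hour group session is not an adverse-event interview. No detection rate per contact can be drawn from the documents.
- **That the SAP looks only at mean change.** It does not: it also correlates baseline parenting stress with individual change, compares completers with non-completers and reviews feedback. What is absent is a harms summary.
- **That a worsening parent would be dismissed as a non-responder.** The sentence "Lack of effect of treatment is not considered an event" might suggest this, but rising distress already fits the protocol's broad definition of an event, and worsening is not absence of effect.

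It is also fair to say that this is a small pilot of a psycho-educational programme whose listed risks are modest, and that about 70 participants could not establish safety even with full capture. That stands, and limits the weight of the point. It does not close the gap between the promise of monitoring and the described mechanism.

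**Conclusion.** The point holds in a limited form. The protocol promises monitoring throughout but describes no scheduled adverse-event enquiry applied equally to both arms. Capture rests on staff awareness, which is likely to favour the Immediate arm in months 0 to 3 and the waitlist arm afterwards. The SAP adds no adverse-event or worsening summary. Any recorded count, including zero, would therefore be weak and possibly arm-biased evidence on harms.

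The size of the imbalance cannot be derived from the documents. The inference that capture differs by arm rests on the contact schedule and on the unseen forms containing no common enquiry. If only the progress note asked about events, the imbalance would be larger; if the survey battery asked, it would be smaller. This is a worthwhile, inexpensive improvement. It does not undermine the efficacy analyses.

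**What to change.** **Protocol.** Add one identical question on undesirable experiences since the previous survey, with date and free text, to the existing 3- and 6-month REDCap surveys in both arms. Send positive answers to the Principal Investigator under the existing reporting line.

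**SAP.** Tabulate events by arm, period (baseline to 3 months, 3 to 6 months) and source (survey question or volunteered), giving the number who answered as the denominator. Report by arm the distribution of individual change from time 1 to time 2, with the number worsening, on VAS distress, VAS physical discomfort and the Parental Stress Scale.

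**If collection has finished.** The SAP is dated March 2019 and places randomisation between November 2016 and September 2017, so the 6-month surveys should have closed about a year earlier. In that case, provide the worsening table from data in hand, state passive adverse-event capture as a limitation, and carry the question into the next trial.

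**Cost.** One item at two existing surveys and two short tables, the second using data already collected. The downside is more trivial events recorded and a brief review of each.
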